
#### **Data Sharing:**

After obtaining consent for data sharing, de-identified data collected from demographic, dietary, quality of life, and symptom questionnaires, biochemical testing of urine, serum, radiological and liver biopsy samples of study participants will be made available without cost to researchers and analysts through NIH/ NIDDK data repositories. Data will be submitted at the time of publication. Users must agree to the conditions of use governing access to the public release data, including limitation of research to investigations

consistent with the participants' consent, restrictions against attempting to identify study participants, destruction of the data after analyses are completed, reporting responsibilities, restrictions on redistribution of the data to third parties, and proper acknowledgement of the data resource.

**Study Alternatives:**

Alternatives to the study may be offered at the NIH or at outside medical centers and are routine therapy with interferon for 12 months, being monitored on no therapy, or awaiting results of this or other studies of therapy of chronic delta hepatitis. Patients who choose to enroll in this clinical trial, if not previously treated, may delay therapy with interferon for up to 48 weeks. For this reason, if a patient has advanced disease, the study investigators may choose to recommend treatment with interferon before enrollment (either by the Liver Diseases Branch under protocol 91-DK-0214 or outside of the NIH).

**REMUNERATION/COMPENSATION**

No compensation is offered to study participants.

## Lonafarnib/Ritonavir/Lambda Interferon for Chronic Hepatitis Delta

Patient Name \_\_\_\_\_

### Enrollment Criteria

No	Criteria	Yes/No	Comment
1	Is patient 18 years or above?		Age = _____ years
2	Is anti-HDV present in serum?		Date of sample: ___/___/___
3	Is HDV RNA positive at three time points?		Date of samples: ___/___/___ ___/___/___ ___/___/___
4	Is chronic HDV infection demonstrated by the presence of HDV RNA in serum $\geq$ 6 months, or presence of anti-HDV antibody for $\geq$ 6 months		
5	Is consent form signed?		Date of signature ___/___/___
	The answers to these questions should all be yes for the patient to be enrolled in this study.		

### Exclusion Criteria

No	Criteria	Yes/No	Comment
1	Are any of the last 3 ALT levels > 1000U/L?		
2	Is serum bilirubin > 4 mg%?		Bilirubin =
3	Is serum albumin < 3 gm%?		Albumin =
4	Is protime > 2 seconds prolonged or INR >1.7?		Protime = INR
5	Are triglycerides >500 mg/dL		
6	Is PR or QT c interval prolonged on EKG?		
6	Is there a history of bleeding varices, ascites or encephalopathy?		
7	For females with childbearing potential: Is the patient pregnant, actively breast-feeding, or unable to practice birth control?		Not applicable if patient has had a tubal ligation _____
8	For males: Is the patient able to practice birth control?		Not applicable if patient has had a vasectomy _____
9	Are there significant other medical illnesses such as CHF, renal failure, transplant, psychiatric dx, and angina?		
10	Has the patient been on systemic immunosuppressive therapy within the previous 2 months?		
11	Does the patient have another form of liver disease in addition to coinfection of HBV and HDV?		
12	Has the patient undergone any experimental therapy or pegylated interferon within 6 months prior to starting the study?		

13	Has the patient had a diagnosis of malignancy within 5 years prior to enrollment with the exception of superficial dermatologic malignancies?		
14	Has patient had active substance abuse in the last one year?		Alcohol, inhaled or injection drugs
15	Does the patient have evidence of HIV co-infection?		Date of test: date __/__/__
16	Is AFP > 200 ng/ml and does the ultrasound/MRI/CT show evidence of a mass in the liver?		AFP = _____ US/MRI/CT date __/__/__
17	Is the patient currently on statin medications?		
18	Is the patient currently on medications that would alter metabolism of ritonavir?		Alpha-1-adrenoreceptor antagonist Antiarrhythmic medications Pimozide Sildenafil Sedative and hynotics Ergot St. John's Wort

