### ***Exclusion Criteria:***

1. Decompensated liver disease, defined by bilirubin  $>4\text{mg/dL}$ , albumin  $<3.0\text{ gm/dL}$ , prothrombin time  $>2$  sec prolonged, or history of bleeding esophageal varices, ascites or hepatic encephalopathy. Laboratory abnormalities that are not thought to be due to liver disease may not necessarily require exclusion. Patients with ALT levels greater than  $1000\text{ U/L}$  ( $>25$  times ULN) will not be enrolled but may be followed until three determinations are below this level. Patients with an absolute neutrophil count  $<1000/\text{dL}$  and platelets  $<75,000/\text{dL}$  will be excluded from the study as well.
2. Pregnancy, active breast-feeding, or inability to practice adequate contraception, in women of childbearing potential or in partners of such women. Adequate

- contraception is defined as vasectomy in male sexual partners of female participants, tubal ligation in women, or use of two contraceptive methods such as condoms and spermicide combination with an intrauterine device or Depo-Provera, or Norplant.
3. Significant systemic or major illnesses other than liver disease, including, but not limited to, congestive heart failure, renal failure (eGFR <50 ml/min), organ transplantation, serious psychiatric disease or depression (only if felt to be at high risk by the NIH psychiatric consultation service), or active coronary artery disease.
  4. Systemic immunosuppressive therapy within the previous 2 months before enrollment.
  5. Evidence of another form of liver disease in addition to viral hepatitis (for example autoimmune liver disease, primary biliary cirrhosis, primary sclerosing cholangitis, Wilson disease, alcoholic liver disease, ongoing drug induced liver disease, nonalcoholic steatohepatitis (but not steatosis), hemochromatosis, or alpha-1-antitrypsin deficiency).
  6. Active substance abuse, such as alcohol, inhaled or injection drugs within the previous year.
  7. Evidence of hepatocellular carcinoma. This will be determined on the basis of imaging with ultrasound/ CT scan or MRI performed a maximum of 6 months prior to enrollment. Elevated AFP levels will be evaluated clinically and further imaging may be performed if felt necessary.
  8. Evidence of concurrent hepatitis C infection with positive serum HCV RNA.
  9. Any experimental therapy or pegylated interferon therapy within 6 months prior to enrollment.

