  10. Active, serious autoimmune disease such as systemic lupus erythematosus, ulcerative colitis, Crohn's disease or rheumatoid arthritis, that is in the opinion of the investigators might be exacerbated by therapy with lambda interferon. This will be evaluated at baseline and during follow-up laboratory testing (including blood and urine studies) in addition to described symptoms at each outpatient visit.
  11. Diagnosis of malignancy in the five years prior to the enrollment with exception granted to superficial dermatologic malignancies.
  12. Evidence of HIV co-infection; HIV 1/2 antibody positivity on serum testing.
  13. Concurrent usage of statins as these drugs inhibits mevalonate synthesis, which reduces protein prenylation.
  14. Concurrent usage of moderate and strong CYP3A inhibitors and inducers.
  15. Concurrent usage of alpha 1 adrenoreceptor antagonist, antiarrhythmic, pimoziide, sildenafil, sedative and hypnotics, ergot and St. John's Wort due to possible effect of ritonavir on hepatic metabolism of these drugs resulting in potentially life-threatening side effects.

16. Clinically significant baseline EKG abnormalities such as QTc interval >450 ms and/or prolonged PR interval.
17. Uncontrolled elevated triglycerides (>500 mg/dL). Patients on lipid lowering therapy other than statins will be eligible for this study.
18. History of pancreatitis from causes other than gallstone pancreatitis. Subjects with a baseline amylase and/or lipase level >3 ULN will be excluded from the study.
19. Inability to understand or sign informed consent.
20. Any other condition, which in the opinion of the investigators would impede the patient's participation or compliance in the study.

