**The answer to all of the above questions is no:**

---

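### The exclusion checklist conflicts with the numbered exclusion criteria: item 8 is reversed, item 16 is narrower than exclusion 7 when read as one question, and several exclusions are absent or unnamed

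*Combined protocol and SAP*

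**What the plan says.** The numbered list under Study Entry Criteria, Exclusion Criteria has 20 entries. Those that matter here are:

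- **Exclusion 1** includes limits on absolute neutrophil count and platelets.
- **Exclusion 2** covers "inability to practice adequate contraception, in women of childbearing potential or in partners of such women".
- **Exclusion 7** is "Evidence of hepatocellular carcinoma. This will be determined on the basis of imaging with ultrasound/ CT scan or MRI". On AFP it adds: "Elevated AFP levels will be evaluated clinically and further imaging may be performed if felt necessary".
- **Exclusion 10** is active, serious autoimmune disease.
- **Exclusion 14** is "Concurrent usage of moderate and strong CYP3A inhibitors and inducers".
- **Exclusion 18** covers a history of pancreatitis other than from gallstones, and baseline amylase or lipase above 3 times ULN.

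The appended checklist, also headed Exclusion Criteria, has items numbered to 18 (6 is used twice) and ends with "The answer to all of the above questions is no". Item 7, for women, asks "For females with childbearing potential: Is the patient pregnant, actively breast-feeding, or unable to practice birth control". Item 8 asks "For males: Is the patient able to practice birth control", and its comment column allows a not-applicable entry after vasectomy. Item 16 asks "Is AFP > 200 ng/ml and does the ultrasound/MRI/CT show evidence of a mass in the liver", with separate blanks for the AFP value and the imaging date.

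**The concern.** A checklist that requires a no throughout works only if a yes always means excluded, and only if every exclusion has a line. This form appears to break both conditions.

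The exclusions affected are safety exclusions, and the protocol gives reasons for them. Hazards and Discomforts reports testicular toxicity of lonafarnib in rats and monkeys, neutropenia and thrombocytopenia in an early lonafarnib trial, pancreatitis in ritonavir-treated patients with hypertriglyceridaemia, and CYP3A interactions with ritonavir. The Screening section requires contraception in men with partners of reproductive potential until 6 months after dosing. If staff complete the form as written, a patient may be passed whom the numbered criteria exclude, or an eligible patient may be turned away. If staff silently reinterpret an item, the eligibility records will not be consistent with each other.

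**Working it through.** No figure is involved, so the check sets the two lists side by side and applies the all-no rule as a truth table.

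**Item 8 against exclusion 2**

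| Male patient | Answer to item 8 | Form | Exclusion 2 | Agree? |
|---|---|---|---|---|
| Able to use contraception | yes | fails | not excluded | no |
| Unable, partner of childbearing potential | no | passes | excluded | no |
| Unable, no such partner | no | passes | not excluded | yes |
| Vasectomised | not applicable | passes | not excluded | yes |

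The item errs in both directions. Item 7 immediately above asks about being *unable* and works under the same rule, which suggests a drafting slip in item 8.

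**Item 16 against exclusion 7**

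| Finding | Form, read as one question | Form, read as two questions | Exclusion 7 |
|---|---|---|---|
| Imaging evidence of HCC (a mass), AFP above 200 | fails | fails | excluded |
| Imaging evidence of HCC (a mass), AFP 200 or below | **passes** | fails | excluded |
| Mass not judged to be HCC, AFP 200 or below | passes | **fails** | not excluded |
| AFP above 200, no mass | passes | **fails** | not excluded by AFP alone |

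Bold marks disagreement with exclusion 7. Read as one question, the item admits in one case that the criterion excludes. Read as two, that case is repaired, but the form then excludes in two cases where the criterion does not. Neither reading reproduces exclusion 7.

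**Coverage of the numbered exclusions**

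- *No line at all:* the neutrophil and platelet limits (exclusion 1), non-gallstone pancreatitis history (exclusion 18), and amylase or lipase above 3 times ULN (exclusion 18). That is three checks, drawn from two numbered exclusions.
- *Not named, partly covered:* autoimmune disease (exclusion 10) could be recorded under item 9, which asks openly about other significant illness. CYP3A inhibitors and inducers (exclusion 14) fall within item 18, which asks about drugs affecting ritonavir metabolism, but the drugs prompted in its comment column are only those of exclusion 15. HCV RNA (exclusion 8) is likewise not named and could be reached through item 11, on other liver disease.

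**Do other sections fill the gap?** The laboratory list under Screening has no complete blood count, amylase or lipase. These tests are in the routine and pancreatic panels of the Baseline Evaluation, which is done before therapy but is introduced as applying once a patient has been found eligible. The results will therefore exist before dosing, but neither the screening list nor the form prompts anyone to check them against exclusions 1 and 18.

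**The case against.** The strongest reply is that the form does not set eligibility. The numbered criteria do, and nothing in the documents says that the form replaces them. A form that fails nearly every eligible man would soon be noticed, men are separately counselled on contraception at screening, and a reproductive consultation is scheduled. An MRI is done at baseline and is described as a screen for hepatocellular carcinoma. A diagnosed cancer might also be caught by item 13 (recent malignancy) or item 11. Blood counts and pancreatic enzymes are measured before the first dose.

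All of this stands, and it limits the consequence. It does not remove the contradiction. An item that staff must mentally reverse is a poor eligibility record, and noticing the error in item 8 does not restore lines that are missing elsewhere.

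A reader might also infer more than the text supports:

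- *That item 8 misclassifies every man.* It does not. Vasectomised men are not applicable, and a man unable to use contraception who has no partner of childbearing potential is passed correctly.
- *That item 16 admits any patient with a liver mass and AFP of 200 or below in breach of the protocol.* Exclusion 7 concerns evidence of hepatocellular carcinoma, and a mass alone is not that.
- *That autoimmune disease and CYP3A drugs are missing outright.* Items 9 and 18 are worded openly enough to reach them. What is missing is the name.
- *That the form alone decides who is dosed.* The documents do not say so.

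**Conclusion.** The point holds as an internal inconsistency between an enrolment form and the criteria it is meant to apply. Item 8 is reversed under the form's own rule, and this does not depend on interpretation. Item 16 passes imaging evidence of hepatocellular carcinoma with AFP of 200 ng/ml or below, on the assumption that it is answered as a single question. Three checks have no line, and at least two further exclusions are unnamed and only partly covered.

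The size is qualitative: wrong or inconsistent eligibility decisions where the form is completed literally. How often that would happen cannot be derived from the documents. It depends on how far staff work from the form and how far from the numbered list. No endpoint, analysis or sample-size figure is affected. The form should be corrected because the affected items are safety exclusions and the correction is cheap.

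**What to change.** Reconcile the checklist with the numbered exclusions, line by line:

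1. Reword item 8 in parallel with item 7, so that inability gives a yes, and state the partner condition of exclusion 2. Keep the not-applicable entry.
2. Make item 16 agree with exclusion 7. If AFP is to be recorded, give it its own line so that the imaging question is answered separately, and state what an elevated value leads to under that criterion.
3. Add lines for the neutrophil and platelet limits, pancreatitis history, and amylase or lipase.
4. Name active autoimmune disease and moderate or strong CYP3A inhibitors and inducers. Do the same for HCV RNA, so that no numbered exclusion depends on a general item.

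Where the form's rule is the one the sponsor intended, amend the numbered criterion instead, so that the two agree. This review takes no position on which threshold or rule that should be.

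The cost is a form revision, plus a protocol amendment only if a criterion itself is changed. No procedure, visit or test is added.

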**The answer to all of the above questions is no:**

---

**SYMPTOM SCALE: Delta Hepatitis**

**Name:** \_\_\_\_\_ **Date:(M/D/Yr)** \_\_\_/\_\_\_/\_\_\_

For the following questions, please respond by circling one of the numbers from 1 to 7. The numbers designate the following answer:

1. All of the time
2. Most of the time
3. A good bit of the time
4. Some of the time
5. A little of the time
6. Hardly any of the time
7. None of the time

1. How much of the time since your last visit have you been troubled by a feeling of abdominal bloating?
2. How much of the time have you been tired or fatigued since your last visit?
3. How much of the time since your last visit have you experienced bodily pain?
4. How often since your last visit have you felt sleepy during the day?
5. How much of the time since your last visit have you experienced abdominal pain?
6. How much of the time since your last visit has shortness of breath been a problem for you in your daily activities?
7. How much of the time since your last visit have you not been able to eat as much as you would like?
8. How much of the time since your last visit have you been bothered by having decreased strength?
9. How often since your last visit have you felt anxious?
10. How often since your last visit have you felt a decreased level of energy?
11. How much of the time since your last visit have you felt unhappy?
12. How often since your last visit have you felt drowsy?
13. How often since your last visit have you been irritable?
14. How much of the time since your last visit have you had difficulty sleeping at night?

15. How much of the time since your last visit have you been troubled by a feeling of abdominal discomfort?
16. How much of the time since your last visit have you had mood swings?
17. How much of the time since your last visit have you been unable to fall asleep at night?
18. How often since your last visit have you had muscle cramps?
19. How much of the time since your last visit have you felt depressed?
20. How much of the since your last visit have you had problems concentrating?
21. How much of the time have you been troubled by itching since your last visit?
- 22.** Since your last visit have you had any excessive hair loss?
23. Since your last visit have you had any rashes?

## Appendix 2

### Microbiome Monthly Intake Questionnaire: Delta Hepatitis

Name: \_\_\_\_\_ Date: (M/D/Yr) \_\_\_\_/\_\_\_\_/\_\_\_\_

1. Over past month, have you taken any new antibiotic medications prescribed by a doctor? Yes [ ] No [ ]

If yes, when was the last time you took the antibiotic? \_\_\_\_\_

Name of antibiotic \_\_\_\_\_

Duration of treatment \_\_\_\_\_

2. Over past month, have you taken any probiotics? Yes [ ] No [ ]

If yes, when was the last time you took probiotic? \_\_\_\_\_

Name of probiotic \_\_\_\_\_

How long have you been taking probiotics? \_\_\_\_\_

3. Over past month, have you eaten any yogurt? Yes [ ] No [ ]

If yes, when was the last time you ate yogurt? \_\_\_\_\_

Name of yogurt \_\_\_\_\_

Does yogurt have probiotics in it? Yes [ ] No [ ]
